5.1.3 Participant Exclusion Criteria

The participant must be excluded from participating in the trial if the participant:

1. Has concurrent extra-vesical (i.e. urethra, ureter or renal pelvis) urothelial cell carcinoma of the urothelium. Patients who have involvement of the prostatic urethra with urothelial cell cancer (TCC) that was visibly completely resected and no evidence of stromal invasion of the prostate remain eligible.
2. Evidence of tumour-related moderate/severe hydronephrosis unless stented or with nephrostomy to preserve renal function.
3. Extensive or multifocal bladder carcinoma in situ (CIS) precluding curative chemoradiotherapy.
4. Bulky T3/T4a tumours unsuitable for curative treatment (i.e. > 10 cms in any dimension); node positive disease.

5. Evidence of distant metastatic disease on CT chest/abdomen/pelvis performed within 42 days prior to study entry. Patients with pelvic lymph nodes deemed to be 'positive' are not eligible for the study unless histological confirmation of the largest most suspicious node is negative for malignancy. Patients with known CNS metastatic disease are excluded from the study
6. Prior pelvic radiotherapy
7. Has had prior intravenous chemotherapy, targeted small molecule therapy, or radiation therapy for treatment of bladder cancer. Prior intravesical use of BCG and mitomycin is permissible.
8. Unsuitable for concurrent cisplatin based chemoradiotherapy based on:
 - CTCAE v.4.03, Grade >2 audiometric hearing loss (25dB in two consecutive wave ranges) if previously performed.
 - CTCAE v.4.03, Grade >2 peripheral neuropathy
9. Is currently participating and receiving study therapy or has participated in a study of an investigational agent and received study therapy or used an investigational device within 4 weeks prior to the first dose of treatment.
10. Has a diagnosis of immunodeficiency or is receiving systemic steroid therapy or any other form of immunosuppressive therapy within 7 days prior to registering the patient. Patients with adrenal insufficiency receiving replacement dose steroids are allowed on the trial.
11. Has a known history of active TB (Bacillus Tuberculosis)
12. Hypersensitivity to pembrolizumab or any of its excipients.
13. Has had a prior anti-cancer monoclonal antibody (mAb) within 4 weeks prior to study Day 1 or who has not recovered (i.e., \leq Grade 1 or at baseline) from adverse events due to agents administered more than 4 weeks earlier.
14. Prior or concurrent known additional malignancy of any site unless disease free for 5 years. Exceptions include basal cell carcinoma of the skin or squamous cell carcinoma of the skin that has undergone potentially curative therapy or in situ cervical cancer, Stage T1a well differentiated prostatic carcinoma in men (Gleason = 3+3, PSA <5)
15. Has any history of active autoimmune disease, Stevens-Johnson syndrome or Guillain-Barre. Exceptions to this are:
 - Patients with a history of autoimmune-related hypothyroidism on a stable dose of thyroid replacement hormone
 - Patients with controlled Type I diabetes mellitus on a stable dose of insulin regimen who are also be eligible for this study
16. Has known history of, or any evidence of active, non-infectious pneumonitis.
17. Has an active infection requiring systemic therapy.

18. Has a history or current evidence of any condition, therapy, or laboratory abnormality that might confound the results of the trial, interfere with the patient's participation for the full duration of the trial, or is not in the best interest of the participant to participate, in the opinion of the treating investigator.
19. Has known psychiatric or substance abuse disorders that would interfere with cooperation with the requirements of the trial.
20. Is pregnant or breastfeeding, or expecting to conceive or father children within the projected duration of the trial, starting with the pre-screening or screening visit through 120 days after the last dose of trial treatment.
21. Has received prior therapy with an anti-PD-1, anti-PD-L1, or anti-PD-L2 agent.
22. Has a known history of Human Immunodeficiency Virus (HIV) (HIV 1/2 antibodies).
23. Has known active Hepatitis B (e.g., HBsAg reactive) or Hepatitis C (e.g., HCV RNA [qualitative] is detected).
24. Has received a live vaccine within 30 days of planned start of study therapy.
Note: Seasonal influenza vaccines for injection are generally inactivated flu vaccines and are allowed; however intranasal influenza vaccines (e.g., Flu-Mist®) are live attenuated vaccines, and are not allowed.

5.1.4 Registering a Patient – General Guidelines

Sites will register eligible patients electronically using the online PCR-MIB electronic data capture (EDC) system. Confirmation of registration will also be provided electronically (via email) as well as, a unique 5-digit patient identification number for the patient.

Full training on the PCR-MIB EDC system will be provided to sites prior to site activation.

Prior to patient registration, the investigator should ensure that all of the following requirements are met:

- The patient meets all inclusion criteria and none of the exclusion criteria should apply.
- The patient has signed and dated all applicable consent forms.
- All baseline assessments and investigations have been performed.
- The eligibility checklist has been completed, signed and dated.
- Ensure any support test/investigation reports to be provided to the Trial Centre are de-identified

N.B. You will NOT be able to register a patient if treatment has commenced or if consent has not been given.

Following registration patients should begin protocol treatment within 10 days. Issues that would cause treatment delays should be discussed with the Coordinating Principal Investigator (CPI).

A patient who withdraws consent prior to commencement of pembrolizumab and chemoradiotherapy may be replaced to ensure 30 patients in total are treated with the combination.

For any queries contact the Centre for Biostatistics and Clinical Trials (BaCT) at Peter Mac.

5.2 Study Assessments

5.2.1 Evaluation during screening period

Screening evaluation (within 6 weeks of treatment start date) shall include:

1. Comprehensive medical history
2. Documentation of concomitant medications at time of screening
3. Full physical examination
4. Documentation of ECOG performance status
5. Vital signs
6. Radiological evaluation with a CT Chest/Abdomen and Pelvis must be performed within 6 weeks of treatment starting
7. Laboratory studies no more than 10 days prior to the treatment start include FBE, UECr, LFTs, TSH and coagulation
8. Pregnancy test in female patients with child bearing potential
9. Cystoscopic evaluation by the participating urologist including a thorough as possible transurethral resection of the bladder tumour, bimanual examination under anesthesia, as well as a biopsy of the base of the resected tumour site. Patients referred from outside with incomplete resections will be considered for re-resection if considered feasible by the urologist prior to chemoradiation. Complete description of the location of tumour, size, morphology, extravesical spread, CIS, ureteric involvement will be provided by the urologist performing the cystoscopy.

5.2.2 Evaluation during chemoradiotherapy period

During the chemoradiotherapy period the following assessments are to be performed within 3 days prior to the start of each week of radiotherapy unless otherwise specified below.

1. Adverse events
2. Vital signs
3. Concomitant medications

4. ECOG performance status
5. Directed physical examination
6. Laboratory tests (FBE, UECr, LFTs) within 3 days of the administration of chemotherapy or pembrolizumab. A TSH, T3, T4 is taken every 6 weeks
7. Documentation of new anticancer therapies
8. Collection of blood and urine samples for biomarker studies (Week 1)

If these assessments have taken place during the screening evaluation (5.2.1) within 10 days of treatment commencement, these do not need to be repeated for the first week of therapy.

Note that biomarker blood and urine samples are to be taken on day 1 of therapy with pembrolizumab prior to therapy, please refer to the PCR-MIB Biomarker Laboratory Manual for further blood sampling information.

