5.3.1.3.1 Administration of cisplatin

Cisplatin chemotherapy will commence on the same day as radiation therapy. After 1000ml sodium chloride 0.9% is administered as prehydration (10mmol MgSO₄ is allowed to be added as per institutional preference), cisplatin 35mg/m² in 1000mL sodium chloride 0.9% will be administered over 60 minutes. Cisplatin is commercially available. Conceivably the co-administration of dexamethasone with the chemotherapy may reduce lymphocyte counts and efficacy of pembrolizumab. Therefore, the dose of dexamethasone administered with chemotherapy will be 4mg IV rather than 8mg unless \geq G2 nausea/vomiting develops. The 5HT3 antagonist palonosetron 0.25mg IV (or equivalent 5HT3 antagonist) will be given prior to cisplatin. Other antiemetic use such as aprepitant and/or olanzapine is permissible. Dexamethasone 4 mg IV premedication given prior to cisplatin is permitted and allowed to continue at dose \leq 4mg orally daily for 2 days after administration. Increase in dexamethasone dose is permitted in discussion with the principal investigator. Urine output measurement is not necessary before cisplatin administration as high urine flow does not appear to be protective.

Cisplatin will be administered weekly during radiotherapy at 7 day intervals

The chemotherapy is to be given preferably at the beginning of each week of treatment and as far as possible on the same day of the week (or within no more than 72 hours) on each occasion throughout the course of treatment.

No more than 6 doses of cisplatin will be administered.

Patients' renal function and myeloid function will be assessed within 72 hours prior to administration of each dose of cisplatin.

The patient should be assessed by the doctor prior to proceeding with each dose of chemotherapy.

Dose modification is described in 5.3.2.1.

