5.3.1.4.3 Administration of pembrolizumab

Pembrolizumab 200mg IV, q3 weekly will be given on the same day as the cisplatin, commencing on day 1 (or within no more than 72hrs) of radiotherapy, and given every 3 weeks (weeks 1, 4, 7, 10, 13, 16 and 19).

Pembrolizumab 200 mg will be administered as a 30 minute IV infusion. Sites should make every effort to target infusion duration to be as close to 30 minutes as possible. However, given the variability of infusion pumps from site to site, a window of -5 minutes and +10 minutes is permitted (i.e., infusion duration is 30 minutes: -5 min/+10 min).

Pembrolizumab will continue after chemoradiotherapy has been completed (weeks 7, 10, 13, 16 and 19) for a total of 7 doses for the whole study, culminating with the 7th dose at week 19 of the study (12 weeks post completion of chemoradiotherapy). Pembrolizumab will continue for up to 7 doses total so long as there is

- no evidence of distant metastatic spread before this time
- no intervening administration of new anti-cancer therapy
- no evidence of locoregional progression
- no radiotherapy administered aside from that dictated in the protocol
- no pembrolizumab related AE severe toxicities as detailed in Table 6, Section 5.3.2.2 that require pembrolizumab to be withheld or discontinued.

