5.3.3 Timing of Dose Administration

Pembrolizumab should be administered on Day 1 of commencement of chemoradiotherapy after all procedures/assessments have been completed as detailed on the Trial Flow Chart (Section 6.0).

Pembrolizumab 200mg IV will be given in weeks 1, 4, 7, 10, 13, 16 and 19. Treatment may be administered up to 3 days before or after the scheduled day of each cycle due to administrative reasons.

In the event of a treatment delay due to an adverse event outlined in Table 6, patients may resume pembrolizumab within 12 weeks of the due dose so long as the toxicity has resolved to Grade 1 or less and the patient is on a dose of 10mg or less of prednisolone or equivalent. Subsequent dosing of pembrolizumab will continue until week 19, but not beyond this regardless of the total number of doses that the patient has received.

All trial treatments should be administered on an outpatient basis unless discussed with the Principal Investigator/Sponsor.

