7.1.2.7 Tumor Tissue Collection and Correlative Studies Blood Sampling

Patients participating in the study will sign for consent for the use of their tissue for correlative biomarker studies. The Biomarker Laboratory Manual gives detailed instructions on specimens required and handling. Biomarker evaluable material includes

Tumour Tissue:	
 1) Formalin fixed paraffin blocks (or slides where block is not available) from resected tumour prior to treatment commencement 2) Formalin fixed paraffin blocks (or slides where block is not available) from any recurrent or residual tumour
-----------------------	---

Blood:	Peripheral blood taken prior to treatment commencement, at week 7 and week 23.
Urine:	Mid-stream urine taken prior to treatment commencement, at week 7 and week 23.

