8.4 Exploratory analysis

Tissue, blood and urine will be collected for biomarker analysis as part of the study. Requirements for biomarkers analysis are described in PCR-MIB Biomarker Laboratory Manual.

Resected tumour specimens will be available from the patients enrolled on the trial. These pre-treatment specimens will be comprehensively profiled for the abundance and composition of tumour infiltrating lymphocytes (CD4, CD8, CD3, CD20 and FoxP3 positive cells) by immunohistochemistry using the state-of-the-art Vectra Automated Imaging system recently acquired by the ONJCRI which enables multiplexed immunohistochemical analysis. Descriptive statistics will quantify individual immune parameters and correlation with response.

Blood samples collected prior to treatment, at the end of chemoradiotherapy, and after 24 weeks will be collected from the patients on the trial. PBMCs will be isolated using Ficoll, and changes in specific immune subpopulations (number/ratio) determined by multi-parameter FACS. Changes in the immune regulatory molecules OX-40/LAG3/PD1/ICOS on T cell subsets will be assessed by flow cytometry. Descriptive statistics will quantify individual immune parameters and correlation with response.

Changes in gene expression in CD3+ cells pre and post-treatment will be determined by RNAseq analysis to assess for gene expression changes associated with immune activation [9]. Descriptive statistics will quantify individual immune parameters and correlation with response.

Finally, to independently monitor B cell responses, pre- and post-treatment serum samples from the 30 trial patients will be analysed using CT100 microarrays for changes in titres of 100 cancer-testis auto-antibodies [10]. Descriptive statistics will quantify individual immune parameters and correlation with response.

Other immune endpoints potentially measurable using the biomarker resources from the trial include but are not limited to circulating DNA, antibody titres, peripheral blood markers of immune change and urine detectable immunological markers.

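### The baseline biomarker draw is tied to the first pembrolizumab dose, not to the first trial treatment, so a sample analysed as pre-treatment can follow the start of radiotherapy

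*Combined protocol and SAP*

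**What the plan says.** Section 5.2.2 lists the first biomarker blood and urine collection at Week 1 and adds: "Note that biomarker blood and urine samples are to be taken on day 1 of therapy with pembrolizumab prior to therapy". Its general window for assessments is "within 3 days prior to the start of each week of radiotherapy unless otherwise specified below".

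Three sections govern when the treatments start:

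- Section 5.3.1.3.1 starts cisplatin on the first radiotherapy day. It permits dexamethasone 4 mg IV beforehand and up to 4 mg orally daily for the next 2 days.
- Section 5.3.1.4.3 puts pembrolizumab on the cisplatin day, "commencing on day 1 (or within no more than 72hrs) of radiotherapy".
- Section 5.3.3 puts the first pembrolizumab dose on Day 1 of chemoradiotherapy, once the flow-chart assessments are done, and then says: "Treatment may be administered up to 3 days before or after the scheduled day of each cycle".

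The collection and analysis sections describe an untreated baseline. Section 7.1.2.7 has "Peripheral blood taken prior to treatment commencement, at week 7 and week 23", with the same timing for urine. Section 8.4 has "Blood samples collected prior to treatment, at the end of chemoradiotherapy, and after 24 weeks". For the third sample, Section 5.2.4 uses the end-of-treatment visit, at week 23 or whenever the patient stops.

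**The concern.** The blood analyses in Section 8.4 compare later samples with this first one: immune-cell subpopulations, regulatory molecules on T cells, gene expression in CD3+ cells and auto-antibody titres. If the reference sample is already treated, the estimated change is shifted by whatever treatment did before the draw.

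The protocol itself gives grounds to expect such a shift. Section 5.3.1.3.1 says: "Conceivably the co-administration of dexamethasone with the chemotherapy may reduce lymphocyte counts and efficacy of pembrolizumab". Section 4.2 adds that chemotherapy may deplete immune effector cells and that radiation may stimulate an immune response. If dexamethasone had already lowered lymphocyte counts at baseline, a later fall would be understated or a later rise overstated.

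Section 8.4 has no rule to identify such patients, so they would be pooled with untreated ones. A missed baseline cannot be collected again.

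**Working it through.** The plan states no figure to reproduce. The check is a comparison of sections plus a count of the exposure that the windows allow.

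**Step 1: which therapy does the 5.2.2 note mean?** Section 5.2.3 uses parallel wording for the Week 7 sample, again placing it before therapy. By then the patient has had about six weeks of chemoradiotherapy, so the phrase there can only mean before that pembrolizumab dose. The natural reading at Week 1 is the same. The general window in 5.2.2 does not override this, because it yields to anything specified further down and the note is such a specification.

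**Step 2: what can precede the draw?** Inputs: 2.00 Gy once daily, five fractions a week (5.3.4.7.1); 72 hours (5.3.1.4.3) or 3 days (5.3.3); dexamethasone as in 5.3.1.3.1. I assume consecutive weekday fractions and a draw just before pembrolizumab.

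| Case | Possible exposure before the draw |
|---|---|
| All three treatments start the same day | No earlier-day treatment. That day's fraction and dexamethasone may come first, because no order is stated. |
| Pembrolizumab 72 h after radiotherapy starts, kept on the cisplatin day (5.3.1.4.3) | 3 × 2.00 = 6 Gy, or 4 × 2.00 = 8 Gy if that day's fraction comes first. Same-day dexamethasone is possible. |
| Pembrolizumab 72 h after radiotherapy starts, cisplatin left on the first radiotherapy day (5.3.1.3.1, with the 5.3.3 window) | The same 6 to 8 Gy, plus one cisplatin dose and up to 4 + (2 × 4) = 12 mg dexamethasone. |
| Pembrolizumab ahead of the other treatments (5.3.3 window) | None. |

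The second and third cases differ because 5.3.1.3.1, 5.3.1.4.3 and 5.3.3 do not fit together. If cisplatin starts on the first radiotherapy day and pembrolizumab shares the cisplatin day, the 72-hour allowance has nothing to act on at the first dose. Those sections must be reconciled. Which dosing order is right is not a matter for this review.

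**Step 3: compare with the analysis.** In the second and third cases, a site that follows 5.2.2 breaches the timing in 7.1.2.7 and supplies 8.4 with a sample that does not match its description.

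**Step 4: how many patients?** The documents do not say how often the windows are used. As pure illustration, 10% to 30% of 30 patients would be 3 to 9. Nothing in the documents supports that range, and the conclusion does not depend on it.

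**Step 5: the third sample.** Week 23 in 7.1.2.7 and the 24 weeks in 8.4, for which no starting point is given, differ by about 1 week if both count from treatment start. For patients who stop early, flow-chart note j sets the end-of-treatment visit 28 days after last treatment. The extreme is a patient whose whole treatment ends in week 1: 1 + 4 = week 5, which is 23 − 5 = 18 weeks before the scheduled draw. Stopping pembrolizumab alone would not produce this, because Section 5.3.2.2 lets cisplatin and radiation continue.

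**The case against.** The strongest reply is that the rule is already there. Section 7.1.2.7, which deals with biomarker collection, requires blood and urine before treatment commences, and 8.4 repeats it. A late draw would be a breach of those sections, not something the design calls for. On schedule all three treatments begin on one day, and 5.3.3 places pembrolizumab after the flow-chart procedures, which include the Week 1 biomarker samples. The Biomarker Laboratory Manual, to which the protocol refers for sampling detail, may fix the order of events and the recording of draw times.

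Much of this stands. A reader might infer that the plan deliberately sets a treated baseline; 7.1.2.7 rules that out. A reader might also infer that using the 72-hour window always puts a full cisplatin dose and three days of dexamethasone before the draw. That is not supported either, because 5.3.1.4.3 keeps pembrolizumab on the cisplatin day. The protocol's remark about lymphocyte counts is itself hedged.

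What the reply does not remove is the conflict. Site staff following the visit instruction in 5.2.2 receive a different anchor from the one in 7.1.2.7. Placing pembrolizumab after the assessments does not place the radiotherapy fraction or the premedication after them. The manual may help, but the protocol should agree with its own analysis section.

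On the third sample, drawing at the end-of-treatment visit is an ordinary choice. Removing early stoppers from the week 23 comparison would restrict it to patients who stayed on treatment, so exclusion by rule is not a clear gain.

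**Conclusion.** The concern holds as a conflict between sections. The 5.2.2 note anchors the baseline to pembrolizumab, and the permitted windows let that dose follow the start of radiotherapy, so the draw can come after about 3 fractions (6 Gy). It can also follow same-day dexamethasone. Earlier-day cisplatin and dexamethasone come into play only if pembrolizumab is separated from cisplatin, a point on which the sections disagree.

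The 6 Gy assumes the full 72 hours and consecutive weekday fractions. The share of patients affected and the size of any shift in the immune measures cannot be derived from the documents.

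The consequence is confined to descriptive exploratory work on blood and urine in at most 30 patients. Tumour profiling uses the pre-treatment resection. The toxicity endpoint, the response and survival endpoints, the stopping rule and the sample size are untouched. The third-sample inconsistency is a smaller matter of the same kind: about a week between sections in the usual case, with week 5 as an extreme. Its timing can still be linked to outcome, because patients who stop for progression or toxicity are sampled earlier and 8.4 relates these measures to response.

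**What to change.** - **Section 5.2.2 (and the flow chart):** replace the note with: *Baseline biomarker blood and urine are drawn before the first trial treatment of any kind, whether radiotherapy, cisplatin or its premedication, or pembrolizumab.* Align the Biomarker Laboratory Manual if it repeats the current rule.
- **Data collection:** record the date and time of the draw against the date and time of first treatment.
- **Section 8.4, baseline:** flag any baseline drawn after first treatment, and show the change analyses with and without those patients.
- **Third time point:** state it in 5.2.4, 7.1.2.7 and 8.4 as the week 23 / end-of-treatment visit. Report samples from patients who stopped early by actual week instead of excluding them by rule.
- **Sections 5.3.1.3.1, 5.3.1.4.3 and 5.3.3:** reconcile what they say about the relative timing of the first pembrolizumab and cisplatin doses.

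The cost is a few sentences and a time field if one is not already collected. No samples or visits are added, and the sampling and analysis changes do not alter treatment. With few patients, the analysis without flagged baselines will be less precise, which is why both versions should be shown.
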